Prior to obtaining PSA specimens, the degree of study drug adherence must be ascertained by PCPT staff. **This is extremely important because non-adherence immediately prior to specimen collection will affect the accuracy of the PSA Index. Non-adherence to the study drug that is not reported to PCPT staff may result in an unnecessary recommendation for prostate biopsy. This information is to be communicated to the participant.** If it is determined that in the two weeks prior to the visit that the participant has not taken any study drug, delay collecting the PSA specimen for two months.

Monoclonal PSA determinations will be performed in the Central Laboratory Facility (CLF) and will be blinded to participants and investigators. For both participants receiving finasteride or placebo, PSA determinations will be reported as either "NOT ELEVATED" or "ELEVATED". A numerical PSA value will be reported on all participants with an "ELEVATED" PSA at annual examination. The reported PSA values for participants receiving placebo will be the measured value. The reported PSA values for participants receiving finasteride will be adjusted by a factor calculated by the Statistical Center (with monitoring by the Data and Safety Monitoring Committee).

The adjustment factor will be calculated by first determining the percentage of placebo-treated participants with elevated PSA. Then, for the finasteride-treated participants, the value of PSA for which the same percentage of participants will be elevated will be identified. This value will be used to calculate the factor for adjusting the PSA for participants treated with finasteride. This method will prevent PSA bias between placebo- and finasteride-treated participants for whom a biopsy is recommended. Details of this procedure and justification can be found in the Background Section of this protocol under "PSA Index".

If the participant has an "ELEVATED" PSA a prostate biopsy (see Section 7.7) is recommended. Decisions regarding appropriate follow-up care for the participant should be based on this PSA value and the clinical judgment of the investigator. If a repeat PSA value is deemed necessary, the test *must* be performed by the Central Laboratory Facility. This is essential as, without knowledge of the participant's actual treatment, a value from an outside laboratory is meaningless.

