  - e. Participants found to have high grade (Grade 2 - 3) Prostatic Intraepithelial Neoplasia (PIN) at the time of biopsy should undergo an immediate rebiopsy. The rebiopsy (using the sextant biopsy technique described in Section 7.7c) must be performed within two months of the prior biopsy. If the repeat biopsy is benign or reveals PIN, the patient will continue on protocol. If this biopsy reveals prostate cancer, however, the patient is removed from protocol treatment per Section 7.14.
- 7.8 After seven years on study, all participants still receiving protocol treatment will undergo transrectal ultrasound and prostate biopsy in accordance with Sections 7.7b, 7.7c and 7.7d.
- 7.9 Development of symptoms of benign prostatic hyperplasia.

During participant on study follow-up, should obstructive symptoms develop to such an extent that the participant requests therapy, the participant should be offered therapy in accordance with standard medical or surgical practice. At the time of such therapy (including medical or surgical therapy), the manner of treatment will be recorded on study forms. One of the options for medical therapy may be finasteride. If finasteride is chosen for therapy, the participant must be evaluated and removed from protocol treatment. For this reason, other forms of medical therapy such as alpha blockade should be encouraged.

- 7.10 Upon the diagnosis of prostate cancer, staging will be accomplished in accordance with standard clinical practice (see Section 19.2). PSA values for these participants who were biopsied because of an abnormal DRE and whose biopsy is positive for prostate cancer will be provided by the Statistical Center when requested by PCPT staff. The reported PSA value for participants receiving placebo will be the measured value. The reported PSA value for participants receiving finasteride will be adjusted by a factor calculated by the Statistical Center (with monitoring by the Data and Safety Monitoring Committee).

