- 7.11 In all participants who undergo a surgical procedure in which prostate tissue is removed (e.g., prostate biopsy, TURP, radical prostatectomy), specimens will be submitted to the Pathology Core Laboratory for centralized pathology review in accordance with Section 12.0 and Appendix 19.4. The Pathology Core Laboratory will also serve as the Prostate Tissue Repository for these specimens. Sera for annual PSA determinations will be submitted to the Central Laboratory Facility; residual sera will be banked for future study in a serum bank to be maintained by the Central Laboratory Facility.
- 7.12 The Data and Safety Monitoring Committee will be charged with monitoring and evaluating potential detection bias during the study's progress. This committee may require interim DHT determinations and/or prostate biopsy (in accordance with Section 7.7) in a sample of participants to determine if such bias is operational.
- 7.13 Adherence.

Participant adherence with the medication regimen as well as the follow-up schedule is critical for proper study completion. Data Managers will contact participants every three months for the study's duration to assure medication adherence as well as to reinforce follow-up visit schedules.

Following randomization, tablet counts will occur every six months, i.e., each time the participant requires a new supply of Study Drug. All adherence information will be recorded on study forms. Details of, and procedures for, the assessments are found in the Study Manual.

7.14 Study Blinding Information and Criteria for Removal from Protocol Treatment:

- a. All participants, Study Centers, pathology and laboratory personnel will be blinded to study treatment.
- b. Laboratory and pathology specimens will be labeled by participant identification number and initials only.
- c. Participants treatment will be unblinded only if the treating physician demonstrates a compelling medical need for this information. The study drug may be discontinued without unblinding the participant.
- d. As study arms will be analyzed using an intent to treat method, participants are never "dropped" from the study.
- e. Participants will be removed from protocol treatment under the following circumstances:
  1. diagnosis of prostate cancer.
  2. initiation of treatment for benign prostatic hyperplasia (BPH) with finasteride or other 5-alpha reductase inhibitor.
  3. seven years following randomization (termination of the study).

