**8.0 TOXICITIES TO BE MONITORED AND DOSAGE MODIFICATIONS**

- 8.1 There will be no modifications to the study drug dose.
- 8.2 For decreased libido, impotence and decreased volume of ejaculate or any clinically acceptable symptoms potentially due to the study drug, participants should be requested to remain on study drug. If they refuse, they may be allowed to discontinue the drug. They should then be reassessed in three months. If the side effect has not resolved, the participants can restart the drug. If the side-effects improve, the participants should be re-challenged with the drug and if the side effect recurs, the drug should be discontinued permanently.

The PCPT will not use the new NCI Common Toxicity Criteria for the reporting of Adverse Drug Reactions/Adverse Events and routine follow-up. Please use the Southwest Oncology Group Toxicity Criteria in Appendix 19.1 for: 1) assessment of all symptoms (including those related to sexual function) for the purpose of reporting Adverse Drug Reactions/Adverse Event and for 2) assessment of symptoms not related to sexual function for routine toxicity reporting. For assessment of symptoms of sexual function for eligibility purposes and routine toxicity reporting, use the following criteria in lieu of those in Appendix 19.1.

Impotence:

- Grade 1 decrease in normal function, able with difficulty to achieve vaginal penetration.
- Grade 3 absence of function, no erections

Loss of Libido:

- Grade 1 minimal decrease in desire for sexual activity, no impact on frequency of intercourse
- Grade 2 moderate decrease in desire for sexual activity, minimal impact on frequency of intercourse
- Grade 3 moderate to severe decrease in desire for sexual activity, moderate impact on frequency of intercourse
- Grade 4 no desire for sexual activity, no intercourse

Ejaculate Volume:

- Grade 1 less than 1/3 reduction in ejaculate volume (as perceived by the participant)
- Grade 2 1/3 to 2/3 reduction in ejaculate volume
- Grade 3 greater than 2/3 reduction in ejaculate volume
- Grade 4 no ejaculate

- 8.3 Unexpected or fatal toxicities (including suspected reactions) must be reported to the Southwest Oncology Group Operations Office, and to the IRB. The procedure for reporting adverse reactions is outlined in Section 16.0.

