- 11.2 BIOPSY PRIOR TO SEVEN YEAR BIOPSY: A special procedure will be implemented to maximize the likelihood that the participants having biopsies prior to their scheduled end-of-study biopsy, for example as a result of positive digital rectal examination or elevated PSA, are comparable between the arms in both numbers and characteristics. Specifically, the finasteride arm PSA biopsy threshold will be adjusted based on experience with finasteride-induced downward shift in the PSA distribution so that approximately the same number of participants will be biopsied due to PSA elevations as in the placebo arm. This procedure is necessary because of the effect of finasteride on lowering PSA levels. If this procedure were not used, that is, if unadjusted PSA values were used as the threshold for biopsy in the finasteride arm, then participants in the placebo arm would have a greater probability of having a biopsy prior to the scheduled seven year biopsy, and therefore the placebo arm would likely have more cancers detected because of the greater number of biopsies.

CRITICAL ASSUMPTION: It is assumed that the finasteride-induced PSA change results in a simple downward shift in the PSA distribution and therefore generally preserves the original ranking of the affected participants.

If the preceding assumption does not hold then there is no basis for an assurance that the finasteride arm PSA threshold control procedure will result in comparable participants in each arm being biopsied prior to the seven year biopsy. The validity of this assumption can be tested by comparing between the arms the characteristics of the participants selected for biopsy based on the PSA threshold. The characteristics compared can include: baseline PSA, race, age, body dimensions, medication adherence rate, quality of life measurements, AUA symptom score, etc.

- 11.3 ADHERENCE/CONTAMINATION AND PSA: Participants in the finasteride arm who take less study drug than allotted could have a PSA level declared as "elevated" due to medication nonadherence since their PSA levels may not be as depressed as participants who are fully adherent. Similarly, it is theoretically possible for participants in the placebo arm who take finasteride (placebo arm contamination) to have finasteride-induced lowered PSA levels which masks a prostate cancer. A finasteride contamination effect is also

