possible in the finasteride arm. Therefore the degree of medication adherence and contamination must be known when performing PSA assessments. The plan is to assess adherence/contamination prior to obtaining PSA specimens and to defer taking a PSA specimen in cases where there is evidence of nonadherence or contamination until there is sufficient adherence and lack of contamination. Thus, the participant is motivated to become adherent and not take open label finasteride. Also, meaningless PSA results are avoided. This strategy requires the following assumption, however:

**CRITICAL ASSUMPTION:** The procedures used to assess adherence in the individual participant at each visit where a PSA specimen is to be obtained are sufficiently sensitive and reliable to detect degrees of nonadherence affecting PSA level interpretation.

- 11.4 **SEVEN YEAR BIOPSY:** It is assumed that approximately 40% of the randomized participants will not have a prostate biopsy following seven years of study treatment and have not had a positive biopsy prior to seven years of treatment. Specifically, it is assumed there will be a 40% loss to biopsy based on the sum of 20% mortality, 15% lost to follow-up, and 5% biopsy refusals. The 20% mortality is based on an assumption that the median age at study entry will be 63 years, with the seven year U.S. (white) all-causes mortality for men that age assumed to be approximately 20%. The 15% lost to follow-up is based on experience with other prevention trials. The 5% biopsy refusal rate is based on the belief that participants who stay on the study drug for seven years will be motivated to find out whether or not they have prostate cancer.

**CRITICAL ASSUMPTION:** It is assumed that the factors affecting loss to biopsy will operate the same in both arms of the study so that the groups of participants who do not have biopsies (deaths, lost, refusal) will be comparable between the arms.

Conformity to the above assumption can be monitored by comparing between the arms the characteristics of the participants who do not have the seven year biopsy and the reason for not having the biopsy.

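### The 7.6b rule for deferring a PSA is narrower than 11.3 intends, so a finasteride-arm man who has just restarted drug is drawn at once, indexed as fully suppressed, and counted in the adjustment factor

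*Supplement*

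**What the plan says.** **Treatment Plan, 7.6b.** Staff must establish adherence before each specimen: "Prior to obtaining PSA specimens, the degree of study drug adherence must be ascertained by PCPT staff". The section warns that nonadherence just before the draw disturbs the PSA Index and can lead to a needless biopsy recommendation. Its only instruction for acting on that information reads: "in the two weeks prior to the visit that the participant has not taken any study drug, delay collecting the PSA specimen for two months". The adjustment factor comes from the percentage of placebo men with an elevated PSA; then, "for the finasteride-treated participants, the value of PSA for which the same percentage of participants will be elevated will be identified". No adherence condition is attached to that group. Only values from men off treatment are left unadjusted.

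**Statistical Considerations, 11.3.** The risk is put in terms of partial dosing: "Participants in the finasteride arm who take less study drug than allotted could have a PSA level declared as" elevated, because their PSA may be less depressed. The plan is to "defer taking a PSA specimen in cases where there is evidence of nonadherence or contamination until there is sufficient adherence and lack of contamination". The protocol text does not define sufficient adherence.

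**Toxicities, 8.2.** A man troubled by side effects may stop the drug and is reassessed at three months. "If the side-effects improve, the participants should be re-challenged with the drug". If they have not resolved, he may also restart.

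**Statistical Considerations, 11.2.** Men biopsied before year seven should be comparable between arms in number and in characteristics.

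**The concern.** The rule that sites carry out tests only whether any tablet was taken in the last fortnight. A man who stopped for three months under 8.2 and restarted a few days before his annual visit passes that test. His PSA may still be close to its untreated level, yet it is adjusted as though finasteride had lowered it by the full amount.

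Two things follow. He may receive a biopsy recommendation that full suppression would not have produced. And because the factor matches the percentage elevated across the whole finasteride arm, men like him use up part of the matched quota. The cut rises, and adherent men are prompted a little below the placebo rate. Numbers stay equal between arms, but the characteristics of those prompted, which 11.2 also wants comparable, drift apart.

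**Working it through.** **Rules side by side**

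| Finasteride-arm man at the annual draw | 11.3 | 7.6b |
|---|---|---|
| No drug for two weeks or more | defer | defer two months |
| Restarted days ago after a stop under 8.2 | defer until adherence is sufficient | draw now, index as suppressed |
| Missed some tablets | defer if evidence of nonadherence | draw now, index as suppressed |

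**Is the second row under-suppressed?** The Drug Information section (3.1) says DHT is back at baseline about two weeks after stopping. For PSA it gives reductions of 22.9% at 3 weeks, 15.1% at 6 weeks and 31% at 24 weeks, from a small study of men with metastatic cancer. The Background (PSA Index) uses 48% at Year 1. Incomplete suppression soon after a restart is therefore plausible, but no figure fits this population directly.

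**The plan's own figure.** (1 - 0.48) x 4.0 = 2.08, which the PSA Index section gives as 2.

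**Effect on the matched cut.** Inputs from the documents: 48% reduction when adherent; 5.2% or 9.2% of men at or above 4.0 (PSA Index section, used as a proxy for the placebo rate q); 9,000 men per arm. Assumptions, none in the documents: lognormal PSA with log-SD 0.6 or 0.9; a share d = 2% or 5% of finasteride men under-suppressed at the draw; their suppression 24% (half) or 40%, so that a fraction b = 0.76 or 0.60 of untreated PSA remains.

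Solve for the measured cut c:

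d x P(PSA >= c/b) + (1 - d) x P(PSA >= c/0.52) = q

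One case in full (q = 5.2%, log-SD 0.6, d = 5%, b = 0.76): the log-mean is ln 4 - 0.6 x 1.626 = 0.411. The solution is c = 2.143. Adherent men: c/0.52 = 4.121, rate 4.69%. Half-suppressed men: c/0.76 = 2.820, rate 14.8%. Check: 0.95 x 4.69% + 0.05 x 14.8% = 5.2%.

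Ranges over both q and both log-SDs (prompts per annual screen if all 9,000 attend, out of 468-828):

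| Suppression | d | Cut c | Adherent men's effective threshold | Adherent / placebo prompt rate | Prompts moved |
|---|---|---|---|---|---|
| 40% | 2% | 2.09 | 4.01 | 0.99 | 3-8 |
| 40% | 5% | 2.10 | 4.03 | 0.97-0.98 | 8-19 |
| 24% | 2% | 2.10-2.11 | 4.04-4.05 | 0.96-0.98 | 11-26 |
| 24% | 5% | 2.13-2.14 | 4.10-4.12 | 0.90-0.95 | 26-62 |

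At 24% suppression, 32-50% of the flagged half-suppressed men would have been flagged anyway, so not every such prompt displaces an adherent man.

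**Against the plan's tolerances.** The largest cut, 2.143, is 2.143/2.08 = 1.03 times the intended one. The PSA Index section seeks an estimate within ±5%, and its 45-52% interval implies cuts of 0.48 x 4 = 1.92 to 0.55 x 4 = 2.20. Rounding 2.08 to 2 makes the initial effective threshold 2/0.52 = 3.85, which in the same model raises adherent prompts by 8-14%. That is more than the shift at issue, and in the opposite direction.

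**The case against.** The strongest reply is that little is left once the safeguards are counted. Men still on a drug holiday meet the two-week trigger. Off-treatment values are not indexed. The investigator may use judgment and order a repeat PSA from the central laboratory, and biopsy is recommended rather than required. Annual rescreening and the seven-year biopsy catch most adherent men just under a shifted cut. The comparisons in 11.2, DHT sampling under 7.12 and the six-monthly monitoring committee review could reveal a drift. The Study Manual holds the adherence procedures and is not shown; it may already be stricter. All of this stands and keeps the point small. None of it changes the rule as written: the monitoring can detect the shift but does not prevent it.

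A reader might infer more than the documents support:

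- *Any man who missed tablets is under-suppressed.* Not shown. In 3.1, 0.04 mg/day, under 1% of the trial dose, lowered DHT to 63% of baseline, with an effect at 24 hours. DHT is not PSA, but this is the only low-dose evidence given, and it points the other way.
- *The 10% planning figure for nonadherence can serve as the share affected.* In 11.7 it is a degree of nonadherence among men with cancer at study end, not a share of men under-suppressed at a draw.
- *Open-label use is uncovered.* For BPH treatment, 7.9 says "If finasteride is chosen for therapy, the participant must be evaluated and removed from protocol treatment", and 7.14e lists "initiation of treatment for benign prostatic hyperplasia (BPH) with finasteride or other 5-alpha reductase inhibitor" as a ground for removal. Only undisclosed use or use for other reasons remains.
- *The indexing of nonadherent men contradicts Amendment #5*, whose notice speaks of men determined to be adherent. An amendment notice is not operative text, and I draw nothing from the difference.

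**Conclusion.** The mismatch between 7.6b and 11.3 is real, and the recently restarted man is its clear instance. The direction follows from matching a percentage on a mixed group: under-suppressed men are over-prompted and adherent men fall slightly below the placebo rate.

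The size is not derivable, because the documents give neither the share of such men nor their PSA. Under the assumed 2-5% and 24-40% suppression, the relative shortfall in adherent men's prompts is about 1-10%, with the cut inside the plan's own tolerance. That tolerance concerns precision, however, while this shift always runs one way. Total prompts stay matched by construction.

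A material bias in the primary comparison would be a stronger reading, and the documents do not support it. The point is a minor inconsistency, worth mending because it is cheap and would spare some men a needless biopsy recommendation. It concerns the protocol text only.

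**What to change.** Amend 7.6b as follows, blinded and identically in both arms:

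1. After any interruption of two weeks or more, draw the PSA only once the participant has had two months of resumed dosing. Apply the same check at the deferred draw.
2. Compute the adjustment factor only from on-treatment specimens that meet this rule.
3. Have the Data and Safety Monitoring Committee compare deferral rates by arm.

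Steps 1 and 2 belong together. Filtering the factor alone, with half-suppressed men still drawn, would leave finasteride-arm prompts 2-4% (at 2% of men) or 5-10% (at 5%) above placebo in the model above.

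Two months is the wait 7.6b already uses. The documents do not show that PSA is fully suppressed by then (the Background's unadopted Design #2 puts nearly the whole fall at six months), so the Statistical Center could check it against the trial's own PSA values by time since restart.

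The cost is wording in 7.6b and the Study Manual, plus a data filter using adherence information already collected. The downside is a few more two-month deferrals, possibly more in the finasteride arm if sexual side effects (decreased libido 4.7% against 1.3% in Figure 1) lead to more stops there. That is the reason for step 3.

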#### 7.7 Management of participants with abnormal DRE and/or "ELEVATED" PSA.

- a. If at any time during follow-up, the participant is found to have a digital rectal examination suspicious for prostate cancer or an "ELEVATED" PSA, it is recommended that the participant undergo transrectal ultrasonography (TRUS) and prostate biopsy. **It is to be emphasized that the PCPT recommends that the participant and physician consider the TRUS and biopsy. The participant should be told of this recommendation and advised to discuss it with his physician when considering options for follow-up.** TRUS and biopsy must be performed within 28 days of the abnormal DRE or notification of an "ELEVATED" PSA. If, for any reason, a TRUS and biopsy is not performed, the Statistical Center should be notified per Section 7 of the Study Manual.
- b. Any hypoechoic lesions noted on ultrasonography should be biopsied as well as any digitally notable lesions in addition to sextant biopsy. If no abnormalities are detected on ultrasound or digitally, sextant biopsy should be performed in accordance with Section 7.7c below. It should be emphasized that each participant undergoing biopsy will have at least six biopsies performed.
- c. Technique of sextant biopsy: Transrectal ultrasound (TRUS) will be performed by a clinician experienced in this procedure. Using sagittal imaging, three core biopsies are obtained from the right and left sides at the level of the base, mid-gland, and apical aspects of the prostate. The needle path should be directed so as to maximize the sampling of the peripheral zone of the prostate as described by Hodge, et al. (49) Good Medical Practice guidelines should be observed at the time of the end-of-study prostate biopsy. Medications that interfere with normal coagulation should be discontinued for an appropriate period of time prior to prostate biopsy.

- d. At the time of TRUS/biopsy, three measurements of prostate size will be recorded: maximum AP height, maximum width and prostate length.
  - e. Participants found to have high grade (Grade 2 - 3) Prostatic Intraepithelial Neoplasia (PIN) at the time of biopsy should undergo an immediate rebiopsy. The rebiopsy (using the sextant biopsy technique described in Section 7.7c) must be performed within two months of the prior biopsy. If the repeat biopsy is benign or reveals PIN, the patient will continue on protocol. If this biopsy reveals prostate cancer, however, the patient is removed from protocol treatment per Section 7.14.
- 7.8 After seven years on study, all participants still receiving protocol treatment will undergo transrectal ultrasound and prostate biopsy in accordance with Sections 7.7b, 7.7c and 7.7d.
- 7.9 Development of symptoms of benign prostatic hyperplasia.

During participant on study follow-up, should obstructive symptoms develop to such an extent that the participant requests therapy, the participant should be offered therapy in accordance with standard medical or surgical practice. At the time of such therapy (including medical or surgical therapy), the manner of treatment will be recorded on study forms. One of the options for medical therapy may be finasteride. If finasteride is chosen for therapy, the participant must be evaluated and removed from protocol treatment. For this reason, other forms of medical therapy such as alpha blockade should be encouraged.

- 7.10 Upon the diagnosis of prostate cancer, staging will be accomplished in accordance with standard clinical practice (see Section 19.2). PSA values for these participants who were biopsied because of an abnormal DRE and whose biopsy is positive for prostate cancer will be provided by the Statistical Center when requested by PCPT staff. The reported PSA value for participants receiving placebo will be the measured value. The reported PSA value for participants receiving finasteride will be adjusted by a factor calculated by the Statistical Center (with monitoring by the Data and Safety Monitoring Committee).
- 7.11 In all participants who undergo a surgical procedure in which prostate tissue is removed (e.g., prostate biopsy, TURP, radical prostatectomy), specimens will be submitted to the Pathology Core Laboratory for centralized pathology review in accordance with Section 12.0 and Appendix 19.4. The Pathology Core Laboratory will also serve as the Prostate Tissue Repository for these specimens. Sera for annual PSA determinations will be submitted to the Central Laboratory Facility; residual sera will be banked for future study in a serum bank to be maintained by the Central Laboratory Facility.
- 7.12 The Data and Safety Monitoring Committee will be charged with monitoring and evaluating potential detection bias during the study's progress. This committee may require interim DHT determinations and/or prostate biopsy (in accordance with Section 7.7) in a sample of participants to determine if such bias is operational.
- 7.13 Adherence.

Participant adherence with the medication regimen as well as the follow-up schedule is critical for proper study completion. Data Managers will contact participants every three months for the study's duration to assure medication adherence as well as to reinforce follow-up visit schedules.

Following randomization, tablet counts will occur every six months, i.e., each time the participant requires a new supply of Study Drug. All adherence information will be recorded on study forms. Details of, and procedures for, the assessments are found in the Study Manual.

7.14 Study Blinding Information and Criteria for Removal from Protocol Treatment:

- a. All participants, Study Centers, pathology and laboratory personnel will be blinded to study treatment.
- b. Laboratory and pathology specimens will be labeled by participant identification number and initials only.
- c. Participants treatment will be unblinded only if the treating physician demonstrates a compelling medical need for this information. The study drug may be discontinued without unblinding the participant.
- d. As study arms will be analyzed using an intent to treat method, participants are never "dropped" from the study.
- e. Participants will be removed from protocol treatment under the following circumstances:
  1. diagnosis of prostate cancer.
  2. initiation of treatment for benign prostatic hyperplasia (BPH) with finasteride or other 5-alpha reductase inhibitor.
  3. seven years following randomization (termination of the study).
  4. ~~intercurrent~~ illness which would, in the judgement of the treating physician, affect assessments of clinical status to a significant degree and/or require discontinuation of drug. **Participants will not discontinue the study drug for other medical events which are not considered to be drug-related (e.g., cardiovascular event, diabetes). This determination will be made by the treating physician. The Data and Safety Monitoring**

